- Use of insulin pump in the last 6 months
- Age ≥ 18 to ≤ 40 years
- HbA1c $\leq 8.5\%$ if measured at screening or available from historical medical report performed within the last 6 months; in absence of a valid HbA1c measurement, average blood glucose estimated from CGM data to be approximately 200 mg/dL or less
- Absence of perimenopausal/menopausal symptoms
- Willingness to keep track of beginning of menstrual cycle
- Willingness to keep track of ingested carbohydrates
- Willingness to not become pregnant during study participation
- Regularly menstruating (at least every month with no missed cycles)
- Only free-cycling participants: willingness to use ovulation kits to confirm ovulation
- Only participants under oral contraceptive therapy: use of monophasic pill, with 3 weeks of active pill and 1 week of placebo
- Willingness to use the study Dexcom G6 during the study
- Participants must have Internet access and computer system that meets the requirements for uploading the study equipment

2. List the criteria for exclusion

- Pregnancy
- Hormonal birth control therapy except monophasic pill contraceptive
- Polycystic ovary syndrome (PCOS) diagnosis
- Current use of steroids
- Concurrent use of any non-insulin glucose-lowering agent (including GLP-1 agonists, pramlintide, DPP-4 inhibitors, SGLT-2 inhibitors, sulfonylureas, metformin)
- Uncontrolled thyroid disease
- Active fertility treatment
- Concomitant disease or condition that may compromise patient safety or ability to follow the protocol including: planned or current dialysis treatment; moderate to advanced nephropathy; known or suspected allergy to medical grade adhesives.
- Severe hypoglycemia or diabetes ketoacidosis (DKA) in the previous 6 months

3. List any restrictions on use of other drugs or treatments.

INSTRUCTIONS: List only those drugs or treatments that are prohibited while on study, not those listed as an exclusion criteria.

None

Statistical Considerations

1. Is stratification/randomization involved?

No

► IF YES, describe the stratification/ randomization scheme.

INSTRUCTIONS:

The stratification factors and/or the randomization plan should be identified. If there is no randomization component or important patient characteristics that will be used in treatment allocation or data analysis, a statement to this effect should be included.

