This observational trial is not powered to a specific outcome. A sample size of 40 females has been chosen with the purpose of being able to compute the Cohen's *d* metric once the trial is completed. Cohen's *d* is defined as the difference between two means divided by a standard deviation for the data (standardized difference between two means), and will serve as effect size to appropriately power the subsequent main trial.

3. Provide a justification for the sample size used in this protocol.

Include sample size calculations or statistical power estimation. If not applicable, please provide explanation.

IRB-HSR# 190046: Glycemic Profiles And Insulin Delivery Across The Menstrual Cycle In Women With Type 1 Diabetes

NCT04665999

Also include the anticipated accrual rate, the accrual goal for the study, including accrual goals by strata if appropriate, adjustments for drop-outs etc. and study duration.

The sample size is determined based on the fact that this study is a pilot trial including two groups (i.e., free-cycling females and females using oral contraceptives).

4. What is your plan for primary variable analysis?

Include primary outcome(s)/predictor variable(s), statistical methods/models/tests to be employed, or descriptive summaries as appropriate. If not applicable, please provide explanation.

The primary variable will be insulin sensitivity (SI) computed using a Kalman filter-based algorithm embedding a model of glucose-insulin dynamics; SI will be tracked over the duration of the menstrual cycle and compared between phases.

5. What is your plan for secondary variable analysis?

Include the following:

--Secondary outcome(s)/predictor variables, statistical methods/models/tests to be employed, or descriptive summaries as appropriate. If not applicable, please provide explanation.
--For phase III studies, the power/precision of the study to address the secondary objective(s).

Secondary variables will include metrics to quantify glycemic variability (e.g., percent time spent in different glycemic ranges, low/high blood glucose indices, coefficient of variation).

6. Have you been working with a statistician in designing this protocol?

Consultation with a professional statistician is highly recommended to ensure good science of the study and facilitate the review process.

No

IF YES, what is their name?

Answer/Response:

7. Will data from multiple sites be combined during analysis?

No

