Participants will be screened and inclusion/exclusion will be reviewed. A urine pregnancy will be performed. The subject will also be asked for their medical history, preferably with a physical exam, will be requested but not required. Height, weight, and vitals may be self-reported. Medical history may be obtained from data collected during prior clinical studies conducted from the past 24 months at CDT. Subjects will also have an HbA1c test completed upon enrollment. If the screening is performed remotely, the pregnancy test will be mailed to the participant. The

IRB-HSR# 190046: Glycemic Profiles And Insulin Delivery Across The Menstrual Cycle In Women With Type 1 Diabetes

NCT04665999

pregnancy test must be negative to proceed in the trial. While optional, participants will be asked to provide 3-months of pre-study personal CGM data.

Eligible participants will start a 3-month home data collection. During data collection, subjects will be asked to use a study-provided Dexcom G6 continuous glucose monitor, personal insulin pump, and a study-provided activity tracker. Participants who are not on oral contraceptive will be asked to use an ovulation kit to confirm ovulation. All participants will be asked to record the carbohydrates consumed each day (i.e. meals, snacks, carbohydrate treatments). Unbolused carbohydrates will be recorded in the Dexcom app or receiver, not in the participant's insulin pump. Participants will also be instructed to record Day 1 of their menstrual cycle each month into the Clue App. Free cycling participants will be asked to enter the monthly ovulation test results in the app as well.

Some study participants have prior use of diabetes data aggregators (e.g., Tidepool, Nightscout) and do want to switch to another data aggregator. The study team did not request that they use Tidepool or Nightscout; however, so not to interrupt their standard of care, the study may access study data stored at Tidepool and Nightscout in order to save it on a UVA server for analysis. This may require participants sharing personal login information to the study team to access data or study participants may share this data with the team.

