If the subject owns a personal laptop device, the participant will be asked to bring it to the visit for the study team to download specific software to be used during data collection if an in person screening is performed; otherwise, the study team will instruct the subject how to download the software from online website or the study team may provide the subject with a memory drive (USB) storing the appropriate resources to be used at home will be provided. Participants will be instructed on how to upload the equipment (i.e. insulin pump, CGM, Activity Tracker, Clue App, etc.). Participants will be asked to provide uploaded data periodically during the data collection period (approximately 1-2 times per month) using a local diabetes device management software (e.g., Dexcom Studio). Subjects will have the option of using their personal smartphone or receive a study smartphone to use in order to collect the data from the devices.

Participants will be asked to wear the study activity monitor during the data collection phase. Participants will also wear the activity monitor to collect information on activity, exercise, heart rate, and sleep. The commercially available app associated with the activity monitor will be placed on the smartphone to facilitate weekly downloading of data.

IRB-HSR# 190046: Glycemic Profiles And Insulin Delivery Across The Menstrual Cycle In Women With Type 1 Diabetes

NCT04665999

The study team will contact the participant via phone/email/text at least one time month to assess:

- Adverse events and device issues
- Review download of CGM and activity monitor to assess occurrence of glucose values <60 mg/dL and >300 mg/dL
- Verify Clue App monthly download – the study team logging into the subject's study account to verify its use and download data

Study Schedule

	Screening	Monthly Monitoring	Final
Study Days	1*	2-90	~90
Visit	1	2,3,4	5
Informed consent	x		
Review study eligibility	x		
Medical history (optional)	x		
Pregnancy test	x		x
Physical exam (optional), height, weight, and vital signs (self-reported)	x		
HbA1c	x		x
CGM use	x		
Activity tracker use		x	
Ovulation test (if applicable)		x	
Record menses in app		x	
Data uploads provided to study team		x	x
Monthly check-ins with staff		x	
Return study equipment			x

* Visit 1 may be split over 2 days

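### The contrast between free-cycling women and oral contraceptive users has no stated analysis, and pill and placebo dates are not recorded, so misdated windows could bias it in a direction that depends on the unknown change in pill users

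*Combined protocol and SAP*

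**What the plan says.** The group contrast is promised three times: in Objectives/Hypothesis as part of the primary aim, in Study Design item 2, and at the end of Study Procedures item 1. Background adds an intention to study whether OC therapy stabilises glycaemic control. Statistical Considerations item 3 rests the sample size on the fact that "this study is a pilot trial including two groups (i.e., free-cycling females and females using oral contraceptives".

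The only primary comparison is in Statistical Considerations item 4: "SI will be tracked over the duration of the menstrual cycle and compared between phases". It defines no phase for either group and gives no method for the group contrast. Item 2 says that a Cohen's d from this study will size the next trial, without saying which two means or which SD.

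On dating the cycle, Study Procedures item 1 says for everyone: "Participants will also be instructed to record Day 1 of their menstrual cycle each month into the Clue App". For one group only it adds: "Participants who are not on oral contraceptive will be asked to use an ovulation kit to confirm ovulation", and "Free cycling participants will be asked to enter the monthly ovulation test results in the app as well". OC users qualify through "use of monophasic pill, with 3 weeks of active pill and 1 week of placebo" (inclusion criteria). The Study Schedule has the row "Record menses in app" and an ovulation-test row, but none for pill or placebo dates.

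**The concern.** Free-cycling cycles have two date anchors and OC cycles have one. The natural phases for an OC user are the active weeks and the placebo week, and nothing collected marks the switch between them. Day 1 of bleeding is the only anchor, and the documents do not say where it falls in the placebo week or how it would be turned into windows.

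If windows are counted from Day 1 and are off by some days, each mixes the two pill states and the measured OC change shrinks towards zero. OC users would then look more stable than they are, which resembles the effect the study sets out to investigate. A between-group Cohen's d would carry the error into the sample size of the next trial.

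**Working it through.** The plan gives no effect size, SD, alpha or power, so there is no stated figure to reproduce. The check is a day count.

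**From the documents.** 21 active and 7 placebo days per pack (inclusion criteria); 40 women, with an even split attempted, so about 20 per group; 3 months of data, so about 3 packs.

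**Assumed, because the documents are silent.** Bleeding Day 1 falls L days after the first placebo pill; SI changes at the pill switch; free-cycling phases are dated correctly; the windows are as shown.

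**Share of the OC change that is measured.** Share = (fraction of placebo days in the bleeding window) − (fraction of placebo days in the comparison window).

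| L | Days 1–7 vs 15–21 (1 − L/7) | Days 1–5 vs 14 days before next bleed | Days 1–7 vs 7 days before next bleed (1 − 2L/7) | Days 1–7 vs 8–28 (1 − 4L/21) |
|---|---|---|---|---|
| 0 | 100% | 100% | 100% | 100% |
| 1 | 86% | 93% | 71% | 81% |
| 2 | 71% | 86% | 43% | 62% |
| 3 | 57% | 59% | 14% | 43% |
| 4 | 43% | 31% | −14% | 24% |

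At L = 2 to 3 the range is 14% to 86%. If SI lags the pill switch by K days, the offset that matters is L − K. An offset of either sign attenuates the change; when L = K there is no error.

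**Direction.** Let r be the true OC change (active minus placebo) divided by the true free-cycling change (luteal minus early follicular), and f the measured share. Observed/true mean contrast = (1 − r·f)/(1 − r). For Days 1–7 vs 8–28 at L = 2 and 3 (f = 0.62 and 0.43):

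- r = 0.5: 1.38 and 1.57 (inflated)
- r = 0.25: 1.13 and 1.19 (inflated)
- r = 0: 1.00 and 1.00 (unbiased)
- r = −0.25: 0.92 and 0.89 (reduced)

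This concerns the mean contrast. If the OC changes average zero but vary between women, misdating also shrinks their spread, so a standardised d can still move.

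**Against random error.** If both groups truly change by 0.5 SD, the spurious group d is 0.5 × (1 − share). For shares of 86% to 14% that is 0.07 to 0.43. The 95% half-width for a between-group d of 0.5 with 20 per group is 1.96 × √(2/20 + 0.5²/80) = 0.63.

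**Carry-over, illustration only.** With a true d of 0.5, two-sided 0.05 and 80% power, 63 per group are needed. At L = 3, inflation by 1.19 (r = 0.25) would plan 45 per group with 66% true power; inflation by 1.57 (r = 0.5) would plan 26 with 44%.

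**Does dating by pill remove the problem?** Only if SI does not lag. All active days against the full placebo week, dated by pill, retain 1 − 4K/21: 81%, 62% and 43% at K = 1, 2, 3. Placebo days 4–7 against active days 8–21 retain 100% for K = 0 to 3, and 3/4 = 75% at K = 4.

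**Bleeding dates alone.** Days 1–3 against 15–21 retain 100% when L − K is 0 to 4. They retain 67% at an offset of 5, and 33% at an offset of −2 (for example L = 0, K = 2).

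**The case against.** The strongest objection is that the windows, L and K are the reviewer's own. The plan never says that OC phases will be counted from Day 1, and results from 93% to −14% illustrate a problem without sizing it. This stands: the magnitude is unknown.

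A reader might infer that the missing dates will exaggerate the benefit of OC therapy. The documents do not support that. Inflation of the mean contrast needs a nonzero OC change in the same direction as the free-cycling change. If OC therapy flattens SI, there is little to attenuate. Error in dating ovulation would attenuate the free-cycling change and could pull the contrast the other way.

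A reader might also infer that nothing can be done once the data are in, or that pill dates alone guarantee an unbiased contrast. Neither follows. Bleeding-anchored windows named in advance work under a stated condition, and pill-dated full weeks are still attenuated if SI lags.

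Finally, this is a non-randomised pilot, not powered for any outcome, and the illustrated bias is below its random error. That limits the severity. It does not remove the point: the bias is systematic, more women would not reduce it, and an effect size is the pilot's stated product.

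**Conclusion.** The concern holds in a limited form. The documents promise a group contrast, give no analysis for it, and collect no date that separates active from placebo days in OC users. Counting windows from bleeding would attenuate any true OC change unless bleeding and the SI change coincide or the windows are buffered against the offset. The effect on the mean contrast is inflation, none or reduction, depending on an OC change that is not yet known. The figures (14% to 86% of the OC change measured; spurious d of 0.07 to 0.43 with equal true changes of 0.5 SD) rest on a 28-day pack, an SI change at the switch, bleeding 2 to 3 days later and the windows tabulated. They are illustrations, not estimates. It should be fixed, because the remedy is cheap.

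**What to change.** 1. **Study Procedures item 1 and Study Schedule.** Have OC users record the first active-pill day and first placebo-pill day of each pack in the app they already use.

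2. **Statistical Considerations item 4.** Keep the sentence and add: for each woman, the change in mean SI between two phases named before analysis, averaged over her cycles. Free-cycling: luteal minus early follicular, dated from ovulation tests and menses. OC: active minus placebo, dated from pill records. Report the between-group difference in mean change with a 95% CI, as an unadjusted estimate from non-randomised groups. Because SI may lag the switch, drop the first days of each OC window, for example placebo days 4–7 against active days 8–21, and give the full-week windows as a sensitivity analysis.

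3. **Statistical Considerations item 2.** Name the means and the SD behind each Cohen's d and give a 95% CI.

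If pill dates cannot be collected, name bleeding days 1–3 against days 15–21 in advance, and state that these are correct only if bleeding starts 0 to 4 days after SI changes.

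**Cost.** About 2 entries × 3 packs × 20 women = 120 short entries, plus protocol wording; no extra visits or participants. The buffered windows use fewer days (4 of 7 placebo days), and the contrast stays imprecise and non-randomised.

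### Does an optional, possibly 24-month-old medical history let ineligible women into the study?

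*Combined protocol and SAP*

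**What the plan says.** Three parts of the combined protocol and SAP bear on this.

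- **Inclusion/Exclusion Criteria, item 2.** There are nine exclusions. Some depend on the woman's present state, such as "Current use of steroids", the use of non-insulin glucose-lowering agents, active fertility treatment and thyroid control. One looks back over a fixed window: "Severe hypoglycemia or diabetes ketoacidosis (DKA) in the previous 6 months".
- **Study Procedures, item 1.** The screening paragraph opens with "Participants will be screened and inclusion/exclusion will be reviewed". It continues: "The subject will also be asked for their medical history, preferably with a physical exam, will be requested but not required". It then adds: "Medical history may be obtained from data collected during prior clinical studies conducted from the past 24 months at CDT". No step for updating a reused history is given. Home data collection is restricted: "Eligible participants will start a 3-month home data collection".
- **Study Schedule.** At Visit 1, "Review study eligibility" is a row of its own, with no optional label. A separate row for the history begins "Medical history (optional".

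**The concern.** Apart from pregnancy, which has its own required test, the exclusions are mostly things one learns by taking a history. If the history can be skipped, or copied from an earlier study, it seems that current drugs and recent events could go unseen. A record more than 6 months old holds no information on the 6-month event window, and a record of any age above zero cannot alone show what a woman takes today.

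Two things would be at stake. One is the screen for recent severe hypoglycemia or ketoacidosis. The other is the primary variable, insulin sensitivity: steroids, other glucose-lowering drugs and thyroid disease could plausibly alter it. With about 20 women per group, a few misclassified women could shift a group mean or widen the SD that enters the Cohen's *d* meant for planning the next trial.

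**Working it through.** The protocol gives no figure to reproduce here, and no sample size, power or error rate depends on the point. The check is mainly a reading of the text, with a little arithmetic on the time windows.

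**Step 1: what an old record can cover.** Inputs are the 6-month look-back (exclusion criteria) and the 24-month limit on reused data (Study Procedures, item 1). A record taken *a* months before screening covers max(0, 6 − *a*)/6 of the look-back.

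| Record age (months) | Look-back covered |
|---|---|
| 0 | 100% |
| 1 | 83% |
| 3 | 50% |
| 6 | 0% |
| 12 | 0% |
| 24 | 0% |

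Ages from 6 to 24 months make up 18/24 = 75% of the permitted range and give no coverage. If record ages were spread evenly over 0 to 24 months (an assumption), mean coverage would be (1/24) × ∫₀⁶ (6 − *a*)/6 d*a* = 3/24 = 12.5%.

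These figures are correct as arithmetic, but they describe calendar months and not women. They measure harm only if the old record is the sole source for the eligibility decision. The protocol does not say how many women have prior-study data.

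**Step 2: is the record the sole source?** Setting the statements side by side:

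| Item | Status in the protocol |
|---|---|
| Review of inclusion and exclusion criteria | Stated for all participants; separate Visit 1 row; not optional |
| Start of home data collection | Eligible women only |
| Medical history | Asked for; optional in the schedule |
| Reuse of prior-study data | Permitted, not required |
| Source of information for the review | Not stated |

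An optional history and a mandatory review can both be carried out as written, so the statements do not contradict each other. The word *also* in the sentence on history presents it as an addition to the review, not as the review itself. Visit 1 may be held in person, by phone or by video, so staff can put questions directly to the woman. A reviewer with only a two-year-old file cannot declare a woman free of current steroids and must ask.

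**Step 3: which criteria are really exposed?** Fewer than the full list. Current contraception has to be known in any case, because it defines the two groups and decides who uses ovulation kits. PCOS is worded as a diagnosis, so an earlier record would miss only one made since. What remains is mainly steroids, glucose-lowering agents, fertility treatment, thyroid control and the 6-month events, together with any concomitant disease that has arisen since the record.

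**Step 4: size if one woman slips through.** The target is up to 40 women, split evenly if possible, so 40/2 = 20 per group. One woman is 1/20 = 5% of a group. If her insulin sensitivity differs from the rest by *k* SD, the group mean moves by *k*/20 SD. For *k* = 1 to 3 (an assumption) that is 0.05 to 0.15 SD. The primary variable is compared between phases of the cycle, and a stable condition is present in all of a woman's phases, so that comparison is less affected. The contrast between groups has no such protection.

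**The case for a change.** The best argument for a change is that the template tells authors to list everything that will be done, and no questioning about current drugs or recent events is listed. The only named source of such information is the history, which is optional and may be out of date. The protocol does set a currency limit elsewhere: a historical HbA1c counts only if it is no more than 6 months old. Later steps might not catch an error either, since the monthly contacts do not list medication and the section on drug restrictions answers that there are none.

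Much of this stands as a remark on documentation. The protocol does not say how these criteria are confirmed when the history is skipped or reused, and one added sentence would do no harm. It does not show that ineligible women would be enrolled. That inference needs the history file to be the only basis for the review, and no part of the protocol says so. The review is listed and compulsory, and asking about the criteria is how such a review is done.

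The safety argument is also limited. The study is observational, gives no study treatment, and uses the woman's own pump with commercially available equipment. Contact at least monthly covers adverse events and glucose readings below 60 or above 300 mg/dL.

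**Conclusion.** No change to the plan is needed. The observation is accurate: the history is optional, may come from studies up to 24 months back, and carries no stated update step. The conclusion that ineligible women can therefore be enrolled does not follow, because eligibility is settled by a separate, compulsory review at Visit 1. The statements are compatible, and the gap is a missing detail about the source of verification that study staff would fill by asking.

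The size of any misclassification is unknown and cannot be derived from the document. The 75% and 12.5% figures should not be read as measures of harm. The shift of 0.05 to 0.15 SD per misclassified woman rests on 20 women per group and an assumed departure of 1 to 3 SD. The conclusion assumes that staff carry out the eligibility review as the protocol states, against every listed criterion. No sample size, endpoint or analysis depends on the point.

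### The SI analysis has no dated record of insulin given outside the pump or of failed delivery, and no rule for the affected days

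*Combined protocol and SAP*

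**What the plan says.** Statistical Considerations, item 4, defines the outcome: "The primary variable will be insulin sensitivity (SI) computed using a Kalman filter-based algorithm embedding a model of glucose-insulin dynamics". It continues: "SI will be tracked over the duration of the menstrual cycle and compared between phases". Item 4 does not list the algorithm's inputs and has no rule for days with incomplete insulin data. Item 2 of the same section states that the study is not powered for an outcome. Its product is a Cohen's d with which to size a later main trial.

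Study Procedures-Biomedical Research, item 1, names the data sources: "subjects will be asked to use a study-provided Dexcom G6 continuous glucose monitor, personal insulin pump, and a study-provided activity tracker". The pump is among the devices to be uploaded, about once or twice a month. Carbohydrate is logged daily, with a separate route for what the pump does not see: "Unbolused carbohydrates will be recorded in the Dexcom app or receiver, not in the participant's insulin pump".

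The contact held at least monthly has three parts. One asks about adverse events and device issues. The second is: "Review download of CGM and activity monitor to assess occurrence of glucose values <60 mg/dL and >300 mg/dL". The third checks the Clue app. The pump download is in none of them.

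Under Subject Compliance with Study Procedures, item 2, the wear threshold is for the glucose sensor only; missed device downloads also count as non-compliance. The inclusion criteria ask for pump use in the last 6 months, not exclusive use. The question on restricted drugs or treatments during the study is answered with none.

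**The concern.** A model of glucose-insulin dynamics attributes the observed glucose to carbohydrate and insulin, given an SI. If the insulin entered differs from the insulin received, the estimated SI absorbs part of the difference. The plan recognises that the pump is an incomplete record of carbohydrate and provides for it, but makes no matching provision for insulin.

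Two kinds of event matter. In the first, insulin is received but not recorded, for example injected by pen or syringe. In the second, insulin is recorded as delivered but does not arrive, as when an infusion set fails. They push SI in opposite directions.

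At stake are the phase comparison in item 4 and the effect size passed to the main trial. Errors unrelated to phase enlarge the standard deviation and so tend to shrink Cohen's d. Errors that cluster in one phase bias the contrast itself. The time and amount of an unlogged injection cannot be reliably reconstructed after data collection.

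**Working it through.** The plan gives no figure on this point, so there is none to reproduce. The first check is textual and the second is an illustration of size.

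**1. Which events would the planned records show?**

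| Event | Pump upload | Monthly contact | Rule in item 4 |
|---|---|---|---|
| Carbohydrate without a bolus | No | Not needed: logged in the Dexcom app or receiver | Not stated |
| Day or hours off the pump | Likely, as low or absent delivery | Possibly, as a device issue | None |
| Infusion-set failure | Not if silent: insulin is counted as given | Possibly, if noticed and remembered | None |
| Insulin by injection or another route | No | Not asked | None |

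The last two rows are the gap. Where the monthly contact does pick up an event, no date, time, amount or link to the SI analysis is specified.

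**2. How large could the error be?**

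Assumptions, none of them from the documents: a day's estimated SI is proportional to 1/(recorded insulin), 45 U are received per day, and a phase has 14 days (7 for a short phase). Then

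- multiplier on the day's SI = insulin received / insulin recorded
- shift in the phase mean = k × (multiplier − 1) / D, for k affected days out of D

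Insulin received but not recorded, k = 1, D = 14:

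- 4 U: 45/41 = 1.098; 9.8%/14 = +0.7%
- 8 U: 45/37 = 1.216; 21.6%/14 = +1.5%
- 12 U: 45/33 = 1.364; 36.4%/14 = +2.6%
- half the day's insulin: 1/(1 − 0.5) = 2; 100%/14 = +7.1%, or 100%/7 = +14.3% in a 7-day phase

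Insulin recorded but not delivered, k = 1:

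- half the day's insulin: multiplier 1 − 0.5 = 0.5; −50%/14 = −3.6%, or −50%/7 = −7.1% in a 7-day phase

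Pooling cycles dilutes one bad day. Over 2.5 phases of 14 days (35 days, also an assumption), the four unrecorded cases become 9.8%/35 = 0.3%, 21.6%/35 = 0.6%, 36.4%/35 = 1.0% and 100%/35 = 2.9%.

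The two errors can also offset. If a set fails and the same amount is then injected, insulin received equals insulin recorded over the day and the multiplier is 1, although the timing is wrong.

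**3. What cannot be computed.** The documents give no frequency of such days, no distribution over phases and no SD of SI. The net effect on the phase contrast or on Cohen's d therefore cannot be derived.

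**The case against.** The plan is not silent. The monthly contact asks about device issues, and an infusion-set failure or pump interruption is one. Participants are asked to call about medical issues. Data aggregator records may be available for some women. Pump uploads are required, and a day off the pump should appear in them as low or absent delivery. All of this stands. A reader might infer that nothing records these events or that all the information is lost, and the documents do not support that. What remains uncovered is injected insulin and silent set failure, and the lack of any dated, structured entry tied to the analysis.

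The SI algorithm is also not described. That it takes insulin as an input is a sound inference; that daily SI moves as 1/insulin is an assumption. A Kalman filter may respond less to one bad day, and its handling of gaps is unknown.

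A reader might further infer a specific bias: the Background reports more hyperglycemia after ovulation, so off-pump corrections would cluster there, raise apparent luteal SI and hide part of the effect. With an assumed true luteal change of −15%, two luteal days inflated by 20% would give 0.85 × (1 + 2/14 × 0.2) − 1 = −12.6%, and three inflated by 30% would give 0.85 × (1 + 3/14 × 0.3) − 1 = −9.5%. The arithmetic is right but the premise is not in the documents. They do not say that women on pumps correct hyperglycemia off the pump. The example also needs two to three affected days in every luteal phase and none in the comparison phase, and it ignores undelivered insulin, which acts the other way.

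Finally, this is an unpowered pilot in established pump users. That limits the urgency, but the study's stated product is an effect size, and that figure is what noise in SI would distort.

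**Conclusion.** The point holds as a gap in data capture and analysis rules. Apart from an unstructured monthly question on device issues, the protocol has no dated record of insulin given outside the pump or of failed delivery. The pump is missing from the monthly download review, and item 4 does not say what happens to affected days.

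On such days SI may be wrong in either direction. Under the stated assumptions, a single day with a modest unrecorded amount hardly moves a phase mean. A day with half its insulin misrecorded moves it by several percent, and by more in a short phase. Whether the total amounts to noise or to bias depends on frequency and clustering by phase, which the documents do not give. A claim that the luteal effect is systematically hidden would go beyond them.

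The change is worth making because it is cheap and has to be in place before data are collected.

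**What to change.** - **Study Procedures, item 1 (home data collection).** Ask participants to log any insulin not given by the pump, with time, amount and route, and any infusion-set failure or pump disconnection, with start and end. Use the same app or receiver as for unbolused carbohydrate.
- **Study Procedures, item 1 (monthly contact).** Add the pump download to the review, and ask about days with an unusually low recorded insulin total.
- **Statistical Considerations, item 4.** State that logged off-pump insulin enters the SI model. State that periods with failed or unknown delivery, plus a pre-specified insulin-action window afterwards, are set to missing before phase means are taken. Masking only the failed hours is not enough, because insulin acts beyond the hour of delivery and a dynamic model carries the error forward. Report the phase comparison with and without affected days as a sensitivity analysis.

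The cost is a line on the instruction sheet, one checklist item and one analysis rule. The downside is occasional extra logging by participants and some excluded data. No clinical management is changed.
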